13.1.1.4. Interim Analysis

No interim analysis is planned for this study.

13.1.2.4. Safety Reviews

In the event a study pausing rule is met, the medical monitor and the BARDA Pharmacovigilance SME and/or BARDA Medical Officer will convene to discuss and review relevant cases. No pre-planned interim safety reviews will be conducted for this study.

13.1.2.5. Final Analysis

A clinical study report will be written to include all PK and safety data collected throughout the study. For the final analysis, the study database will be monitored, cleaned, and locked per associated study plans. Further details will be specified in the SAP.

13.1.2.6. Exploratory Analyses

No exploratory analyses are planned.

13.2. Sample Size Considerations

The target sample size for randomization for this study is approximately 46 participants, allowing for a 20% dropout rate that would result in approximately 36 evaluable participants (approximately 18 per dosing sequence) within the per protocol population. Additional participants may be randomized if participants are withdrawn prior to receiving one or both doses of study drug (Section 8.2.2).

The sample size was determined for an equivalence test of the ratio of means using two one-sided tests on data from a two-period cross-over design. In the previous PK study of SL administration of atropine (BP-C-19010),⁸ the standard deviation for the dose-adjusted log10 difference in high (1.0 mg) versus low (0.5 mg) SL dosing for AUC_{∞} and C_{max} were 0.102 and 0.146, respectively. Since the intra-participant variability in PK parameters between SL and IM administration is unknown, the standard deviations were conservatively multiplied by a factor of 1.25 to determine power and sample size for this study. Corresponding coefficients of variance were estimated as 0.212 and 0.304 for AUC_{∞} and C_{max} , respectively. A sample size of 36 achieves greater than 99% power to test bioequivalence for AUC_{∞} and 86% power for C_{max} at the 0.05 significance level when the true ratio of means is 1.0 and the equivalence limits are 0.80 and 1.25. Even if the true ratio of means are within $\pm 5\%$ of 1.0, the study still maintains 96% and 77% power for AUC_{∞} and C_{max} , respectively.

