A study of SL injection of atropine is included here since it is a useful evaluation of atropine PK, and the atropine dose used was two-fold greater than the 1 mg dose to be used in the current study. Rajpal et al. evaluated 9 healthy male volunteers (mean age 20.8 ± 4.7 years, mean weight 59.67 ± 4.76 kg) administered a single SL injection of 2 mg atropine sulfate (in 0.1 mL).⁷ Three of the participants had $99m$ Tc-labeled diethylene triamine pentaacetic acid added to their injection to monitor the release rate of atropine sulfate. Within 10 minutes, 85% of the injected dose was released from the SL site of injection. This compared to only 24% released at 10 minutes from one participant who received IM atropine. The remaining six participants underwent blood sampling for PK and clinical monitoring for signs of atropinization (heart rate, pupil diameter, and mouth dryness). The peak serum concentration of SL atropine was 20 ng/mL at 15 minutes compared to peak serum concentrations of 6 to 8 ng/mL at 30 minutes following IM administration. All volunteers who received atropine by SL injection showed signs of atropinization by 10 minutes with peak intensity at 30 minutes and persistence of symptoms for nearly 60 minutes. The authors concluded that atropine administered by SL injection achieves clinically important serum levels more rapidly than by IM administration. Adverse events were not reported in this trial.

BARDA conducted, BP-C-19010, a randomized, 3-sequence, 3-period phase I crossover study to assess the bioavailability and PK of a single dose (0.5 mg and 1.0 mg) of 1% ophthalmic

atropine sulfate solution administered SL to 15 healthy adult volunteers.^{8,9} The primary endpoint was evaluation of the bioavailability of each of the two SL doses against a 1.0 mg reference IV atropine dose. Secondary endpoints included the safety and tolerability (xerostomia scale) of atropine sulfate administered SL. Sublingual atropine was safe (no severe AEs or serious adverse events [SAEs] were reported with either dose) and well tolerated, with a single participant reaching maximum xerostomia on a single dosing day. The geometric mean AUC_{∞} was 286.40, 493.81, and 816.47 $\text{min} \times \text{ng/mL}$ for the 0.5 mg and 1.0 mg SL doses and the 1.0 mg IV dose, respectively. Compared to IV administration, the 1.0 mg SL dose produced 0.60 (90% CI: 0.55-0.66) of the overall concentration of atropine over time (AUC_{∞}).

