13.1.2.2. Primary Analysis

Pharmacokinetic parameters AUC_{∞} and AUC_t will be estimated for each participant and route using the noncompartmental method and will be summarized by route of administration using descriptive statistics.

Relative bioavailability of SL administration of atropine sulfate compared to that of IM atropine sulfate will be assessed based on ratios of least-square means and their associated 90% confidence intervals (CIs) generated from linear mixed models including terms for dosing sequence, route, and period as fixed effects, and subject nested within dosing sequence as a random effect. Bioequivalence will be considered met if the 90% CI of the ratio for AUC_{∞} and AUC_t lie within 80.00 and 125.00%.

Additional details of the statistical analyses, methods, and data conventions will be described in the Statistical Analysis Plan (SAP).

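### Does the 0.86 ratio between the two sublingual doses in the previous study undermine the power stated in Protocol 13.2?

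*Protocol*

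**What the plan says.** Protocol 13.2 sizes the trial for two one-sided tests in a two-period crossover. The variability input is "the standard deviation for the dose-adjusted log10 difference in high (1.0 mg) versus low (0.5 mg) SL dosing for" AUC∞ and Cmax, with values 0.102 and 0.146. The reason for borrowing it, and for the factor of 1.25, is given: "Since the intra-participant variability in PK parameters between SL and IM administration is unknown, the standard deviations were conservatively multiplied". The resulting coefficients of variation (CV) are 0.212 and 0.304. With 36 evaluable participants, power is stated as above 99% (AUC∞) and 86% (Cmax) "at the 0.05 significance level when the true ratio of means is 1.0 and the equivalence limits are 0.80 and 1.25". For true ratios within 5% of 1.0, "the study still maintains 96% and 77% power" for AUC∞ and Cmax respectively. No source is given for the ratio itself.

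Protocol 5.3 reports the previous study, "atropine sulfate solution administered SL to 15 healthy adult volunteers". The geometric mean AUC∞ "was 286.40, 493.81, and 816.47" min × ng/mL for 0.5 mg SL, 1.0 mg SL and 1.0 mg intravenous (IV). It adds: "Compared to IV administration, the 1.0 mg SL dose produced 0.60 (90% CI: 0.55-0.66) of the overall concentration of atropine over time". Neither document gives an IM AUC.

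Protocol 13.1.2.2 sets the decision rule, repeated in SAP 11.2.2: "Bioequivalence will be considered met if the 90% CI of the ratio for" AUC∞ and AUCt lies within 80.00 to 125.00%.

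**The concern.** Section 13.2 appears to take half of a result. It uses the spread of the 1.0 mg versus 0.5 mg contrast, widens it by 1.25, and leaves out the centre. The centre can be recovered from Protocol 5.3: after dose adjustment the higher dose gave 0.862 of the AUC∞ of the lower, and a reconstructed 90% confidence interval (CI) excludes 1.0. If one solution by one route can differ by 14%, a 5% allowance for a change of route, site and product looks too narrow.

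The stakes would be real. Equivalence power falls quickly as the true ratio moves towards a limit. At 0.862 more than half of such trials would end with an interval crossing 0.80. The decision rule also has no separate label for that outcome and for an interval lying wholly below 0.80.

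**Working it through.** **Inputs.** From Protocol 13.2: log10 SD 0.102 for AUC∞, factor 1.25, CV 0.212 (AUC∞) and 0.304 (Cmax), 36 evaluable, limits 0.80 and 1.25, one-sided 0.05 for each test. From Protocol 5.3: geometric means 286.40, 493.81 and 816.47; 15 participants.

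**1. The plan's own figures.** The within-participant SD on the ln scale is 1.25 × 0.102 × ln(10)/√2 = 0.208, which gives CV = √(exp(0.208²) − 1) = 0.210. The stated 0.212 is slightly larger, which is harmless. Using 0.212: SD = √ln(1 + 0.212²) = 0.2097; SE = 0.2097 × √(2/36) = 0.0494; df = 34; t = 1.691. Exact power of the two one-sided tests, integrated over the distribution of the variance estimate:

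| True ratio | AUC∞, computed | AUC∞, stated | Cmax, computed | Cmax, stated |
|---|---|---|---|---|
| 1.00 | 99.5% | above 99% | 86.0% | 86% |
| 0.95 | 96.1% | 96% | 76.2% | 77% |
| 1.05 | 96.5% | 96% | 77.1% | 77% |

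The stated powers are delivered under the stated assumptions.

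**2. The figures behind the concern.** Dose-adjusted ratio: 493.81/(2 × 286.40) = 0.862, log10 = −0.0644. Assuming 15 complete pairs, SE = 0.102/√15 = 0.0263 and t(14) = 1.761. The 90% CI is 10^(−0.0644 ± 1.761 × 0.0263) = 0.775 to 0.959. Power at a true ratio of 0.862 is 43.5%. This arithmetic is right.

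**3. What 0.862 measures.** It is SL over SL at two doses, so it describes dose proportionality of the SL route. The ratio in 13.2 is SL over IM at 1 mg each, and this trial has no 0.5 mg arm. The two are linked only through IV:

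- SL:IV at 1 mg = 493.81/816.47 = 0.605.
- SL:IM = 0.605/F, where F is IM:IV. F is not in the documents.
- SL:IM = 0.862 requires F = 0.605/0.862 = 0.70.
- That is the dose-adjusted 0.5 mg SL value against IV: 2 × 286.40/816.47 = 0.702.

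Reading 0.862 as SL:IM therefore treats the 0.5 mg SL arm as if it were the IM arm. Nothing in the documents supports that.

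**4. Why the SD can be borrowed and the mean cannot.** The within-participant SD is a nuisance parameter. Another contrast in the same drug is a reasonable stand-in, and 13.2 states the substitution and adds a margin. The mean of a contrast is specific to the treatments compared.

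**5. Tolerance of the design.** At CV 0.212 and n = 36, AUC∞ power is 75.5% at 0.90, 80.1% at 0.907, 81.3% at 1.10 and 80.3% at 1.102. Only 22 evaluable participants would be needed for 80% AUC∞ power at 0.95. The tighter figures at 36 are those for Cmax, a secondary endpoint. Both AUCs must pass. If AUCt has the same CV and a correlation of 0.8 to 0.99 with AUC∞ (both assumed), joint power at 0.95 is 94 to 96%.

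**6. Reporting.** At a true ratio of 0.862, the AUC∞ interval would cross 0.80 in about 56% of trials; at 0.605 it would lie wholly below 0.80 almost always. Protocol 13.1.2.2 and SAP 11.2.2 base the assessment on ratios with 90% CIs, and SAP 11.2.2 adds subject-specific ratios. The two outcomes can be told apart from the reported intervals.

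**The case for a change.** The strongest opposing case does not need 0.862 to be an estimate of SL:IM. The SL:IM mean is as unknown as its variability. The SD gets a margin of 1.25, while the mean gets only 5%, although equivalence power depends heavily on it. The one cross-route figure available, SL:IV of 0.605, is compatible with SL:IM of 0.95 to 1.05 only if IM:IV is about 0.58 to 0.64 (0.605/1.05 to 0.605/0.95). With assumed IM:IV values of 0.55, 0.65, 0.70 and 0.75, SL:IM is 1.10, 0.93, 0.86 and 0.81, and AUC∞ power is 81%, 91%, 45% and 7%.

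Part of this stands. Section 13.2 would be better with a source for the ratio, or with power shown over a wider range. But the table depends entirely on an IM:IV value that the documents do not give, so it cannot show that the planned ratio is wrong. The dose contrast does not help either, since non-proportionality within one route does not measure uncertainty between two.

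Resizing has the same weakness. A planning ratio of 0.90 is as unsourced as 1.0. Going from 36 to 46 evaluable participants raises AUC∞ power at 0.90 from 76% to 84% and still leaves about 51% at 0.862. That is a choice about enrolling more, and no error would be corrected by it.

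An explicit label for inconclusive results is a matter of preference. A rule declaring the routes not bioequivalent when either AUC interval lies wholly outside the limits would also carry a false-declaration rate of about 5.5 to 7.5% when both true ratios are 0.80 (simulated, correlation 0.99 to 0.8).

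**Conclusion.** The concern does not hold. The 0.862 and its 43.5% power are computed correctly but belong to a different comparison, so they do not contradict the 96% in Protocol 13.2. Using the SD of the dose contrast without its mean is sound. With CV 0.212 and 36 evaluable participants, the stated AUC∞ powers are met (99.5% at 1.0; 96.1% and 96.5% at 0.95 and 1.05), and power stays at or above 80% from about 0.907 to 1.10. This rests on the borrowed SD with its 1.25 margin being adequate for SL versus IM, and it covers AUC∞ alone, since no AUCt variability is given. The true SL:IM ratio remains unknown from these documents. A citation for a value near 1.0 would be welcome, but its absence neither falsifies a stated figure nor affects the validity of the bioequivalence rule.

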13.3. Statistical Considerations

13.3.1. Covariates

Due to the small sample size and cross-over design of this study, analyses adjusted for additional covariates beyond those specified for the primary analysis are not planned.

13.3.2. Multicenter Studies

This is a single center study thus study data will be analyzed as a whole.

13.3.3. Multiple Comparisons and Multiplicity

No adjustments will be made for multiple comparisons.

13.3.4. Subgroup Analyses

Any subgroups requiring more consideration will be discussed in the SAP as needed.

13.3.5. Missing Data

Standard procedures will be used to ensure that the data are as complete and accurate as possible. All descriptive summaries will be based upon all available data, and no imputation will be done.

13.4. Procedures for Documenting Deviations from Planned Analyses

The principal features of the design of this study and of the plan for statistical analysis of the data are outlined in this protocol. Additional details will be included in the SAP before initiating analyses. Any changes to that plan will be documented in the final clinical study report and will be approved by BARDA before being initiated.

14. DIRECT ACCESS TO SOURCE DATA/DOCUMENTS

14.1. Inspection of Records

BARDA, its designees, other authorized representatives of BARDA, Rho or its designees, Allucent or its designees, representatives of the IRB, and/or regulatory agencies may inspect all source documents and records required to be maintained by the site investigator, including but not limited to, medical (office, clinic, or hospital) and pharmacy records for the participants in this study; eCRFs, IRB submissions and approvals, study drug accountability logs, study drug temperature monitoring logs, regulatory documents, correspondence, and all other essential documents. The clinical study site will permit site visits and access to (and when required by applicable law to copy) such records.

The site investigator also agrees to promptly notify BARDA and other authorized representatives of the sponsor of any inspections scheduled by any regulatory authority, or audits by other parties and promptly forward copies of any reports received to BARDA.

14.2. Institutional Review Board

A copy of the protocol, informed consent forms (ICFs), any other participant facing documents, and any proposed advertising/recruitment materials will be submitted to the IRB for written approval. Initial IRB approval and all materials approved by the IRB for this study, including the participant consent form and recruitment materials, must be maintained by the site investigator and made available for inspection.

15. QUALITY CONTROL AND QUALITY ASSURANCE

Quality assurance (QA) includes all the planned and systematic actions that are established to ensure that the clinical study is performed, and the data are generated, documented (recorded), and reported according to International Council for Harmonisation (ICH) Good Clinical Practice (GCP) and local/regional regulatory standards.

To ensure the reliability of study data, the participating site(s) will have a plan in place to describe:

- routine internal quality control (QC) and QA activities for the purposes of measuring, documenting and reporting study conduct, protocol adherence, human subjects' protections, and reliability of the protocol-driven data collected;
- a process for addressing in a timely manner any data quality issues (i.e., collecting, recording and reporting data), systemic issues (i.e., protocol conduct, non-compliance, human subject protections), and implementation of corrective and preventative action (CAPA) procedures.

A quality assurance representative from BARDA (or designee), who is independent of and separated from routine monitoring, may periodically arrange audits of the clinical study by reviewing the data obtained and procedural aspects. These audits may include on site or remote audits and source data checks. Direct access to source documents is required for the purpose of these periodic audits.

15.1. Data Quality Assurance

Data collected at the study site will be entered accurately and contemporaneously by study staff into a 21 CFR 11-compliant, internet-based, remote data entry system, which is backed up nightly. Data will be provided using the participant's unique identification number, not name or initials; Rho will not collect personally identifying information such as the participant's name or social security number. Participants will provide demographic information such as biological sex at birth, race, ethnicity, and age. All elements of data entry (e.g., time, date, verbatim text, and the person performing the data entry) will be recorded within the remote data entry system's audit trail to allow all data changes in the database to be monitored and maintained in accordance with federal regulations. Data collected by the laboratories will be transferred electronically directly from the laboratory to Rho using standard secure data transfer procedures. The analysis datasets will incorporate data from both sources. Data collected by Rho will be held in the strictest confidence and are protected from access that could reveal personal information about any participant in the study.

Clinical data management and data cleaning procedures (e.g., resolving errors and inconsistencies in the data) will be performed in accordance with applicable Rho and/or BARDA standards and validation plans to ensure the integrity of the data. Adverse events (including SAEs) and concomitant medication terms will be coded using the MedDRA and the World Health Organization Drug dictionaries, respectively.

After study monitors verify the data and prior to the final study analysis, the investigator must sign each eCRF at the participant level to confirm the integrity of the data recorded.

After database lock, the study site will receive an electronic copy of all of their site-specific eCRF data as entered into the remote data entry system for the study, including full discrepancy and audit history. Additionally, all of the study's analysis datasets will be sent to BARDA electronically for storage. Rho will maintain a duplicate copy for its records and will upload a copy to the BARDA Clinical Studies Network (CSN) archive.

15.2. Study Monitoring

Site monitoring is conducted to ensure that the rights and well-being of trial participants are protected, that the reported trial data are accurate, complete, and verifiable, and that the conduct of the trial is in compliance with the currently IRB/IEC approved protocol/amendment(s), ICH GCP, and applicable regulatory requirement(s). Clinical monitoring also verifies any critical study procedures are completed following specific instructions in ancillary documents referenced in the protocol.

Monitoring for this study will be performed by BARDA's authorized representatives at Allucent. Details of clinical site monitoring are documented in a monitoring plan. The monitoring plan describes in detail who will conduct the monitoring, at what frequency monitoring will be done, at what level of detail monitoring will be performed, and the distribution of monitoring reports. Monitoring visits will include, but are not limited to, review of regulatory files, accountability records, eCRFs, ICFs, medical and laboratory reports, site study drug storage records, training records, and protocol and GCP compliance. Site monitors will have access to the participating site facilities, study personnel, and all study documentation according to the monitoring plan. Study monitors will meet with site investigators to discuss any problems and outstanding issues, and will document site visit findings and discussions.

15.3. Protocol Deviations

15.3.1. Protocol Deviation Definition

A protocol deviation is any noncompliance with the IRB-approved study protocol, ICH GCP guidelines, or protocol-specific Manual(s) of Procedures (MOPs). Any deviation that affects the rights or safety of the participant or the integrity of the data will be considered a major protocol deviation. Prospective permission to deviate from protocol requirements, also known as protocol waivers or exemptions, will not be granted for this study.

15.3.2. Reporting and Managing Deviations

The site investigator has the responsibility to identify, document, and report deviations. Protocol deviations may also be identified during site monitoring visits or during other forms of study conduct review. All deviations, regardless of the cause, must be documented in accordance with GCP. Documentation at a minimum, will include the date the deviation occurred, the date it was identified, a description of the deviation, whether the deviation resulted in an AE or SAE, and documentation of a corrective action plan. In addition, the site investigator will report noncompliance to the IRB/IEC, as applicable.

Rho, Allucent, and/or BARDA may request discussion with the site investigator to determine the effect of any major protocol deviation on a study participant and his/her further study participation, the effect of the deviation on the overall study, and corrective actions.

16. REGULATORY AND ETHICAL CONSIDERATIONS

16.1. Ethics Review

Before study initiation, the site will obtain IRB approval for this protocol; ICF(s); participant recruitment procedures; written information to be provided to participants; information about payments and compensation available to participants; and any other documents that the IRB may require to fulfill its responsibilities. Any amendments to the protocol will require IRB approval before implementation except for changes necessary to eliminate an immediate hazard to a participant.

IRB review and approval of protocol documents will occur at least annually throughout the enrollment and follow-up of participants, as per applicable regulations and the IRB.

The site investigator will promptly report all unanticipated problems involving risks to participants to the IRB.

The site investigator will notify the IRB of events such as deviations, SAEs, etc. as applicable to the IRB policy.

Participants may be compensated for their participation in this study. Compensation will be in accordance with the IRB's policies and procedures, and subject to IRB approval.

16.2. Ethical Conduct of the Study

The site investigator should conduct the study in accordance with this protocol, the Declaration of Helsinki, current ICH GCP guidelines, US 21 CFR Part 50 (Protection of Human Subjects), and Part 56 (Institutional Review Boards).

16.3. Written Informed Consent

Informed consent is a process that is initiated prior to an individual agreeing to participate in a trial and continuing throughout the individual's trial participation. Before any study procedures are performed, informed consent will be obtained and documented. Potential participants will receive a concise and focused presentation of key information about the study, verbally and with a written consent form. The key information about the purpose of the study, the procedures and experimental aspects of the study, study interventions, study drugs, probability for random assignment to dosing schedules, risks and discomforts, the expected duration of the participant's participation in the trial, any expected benefits to the participant, and alternative treatments and procedures that may be available to the participant. The explanation will be organized and presented in lay terminology and language that facilitates understanding why one might or might not want to participate.

Participants will receive an explanation as to whether any compensation and any medical treatments are available if injury occurs, and, if so, what they consist of, or where further information may be obtained. Participants will be informed of the anticipated financial expenses, if any, to the participant for participating in the study, as well as any anticipated prorated payments, if any, to the participant for participating in the study. They will be informed of whom to contact (e.g., the site investigator) for answers to any questions relating to the research project. Information will also include the foreseeable circumstances and/or reasons under which the

participant's participation in the study may be terminated. The participants will be informed that participation is voluntary and that they are free to withdraw from the study for any reason at any time without penalty or loss of benefits to which the participant is otherwise entitled.

Participants will be informed that records identifying the participant will be kept confidential, and, to the extent permitted by the applicable laws and/or regulations, will not be made publicly available and, if the results of the trial are published, the participant's identity will remain confidential. Participants will be informed whether private information collected from this research and/or specimens will be used for additional research, even if identifiers are removed.

Participants will be informed that the monitor(s), auditor(s), IRB, BARDA, and regulatory authority(ies) will be granted direct access to the participant's original medical records for verification of study procedures and/or data without violating the confidentiality of the participant, to the extent permitted by the applicable laws and regulations, and that, by signing a written ICF, the participant is authorizing such access.

Participants will be allowed sufficient time to consider participation in this research study and have the opportunity to discuss this study with their family, friends or legally authorized representative, or think about it prior to agreeing to participate.

Participants will be informed of the Public Readiness and Emergency Preparedness Act (PREP Act) and the Countermeasures Injury Compensation Program (CICP) ([Appendix 3](#)).

Informed consent forms will be IRB-approved and participants will be asked to read and review the consent form. Participants must sign the ICF prior to starting any study procedures being done specifically for this study. Once signed, a copy of the ICF will be given to the participant(s) for their records.

New information will be communicated by the site investigator to participants who consent to participate in this study in accordance with IRB requirements. The informed consent document will be updated, and participants will be re-consented per IRB requirements, if necessary.

Using the ICF, participants who consent to participate in this study will be asked to consent to permission to be contacted with a request to participate in future clinical studies related to atropine administration.

